##### 15.1.4.1. Multiple imputation for missing at random

Monotone missing data structure will be created as follows: intermediate (non-monotone) missing data will be multiply imputed using the Markov chain Monte Carlo (MCMC) method and assuming MAR and multivariate normality. Transformation of data will only be used if there is a clear deviation from normality. The SAS procedure PROC MI with the MCMC option will be used with seed number=12345.

Then, each component will be imputed with treatment group, DAS28-CRP at baseline and data at previous visit from all DAS28-CRP components as covariates.

Imputation will be repeated 100 times. The DAS28-CRP will then be calculated for each of the multiply imputed data sets from the imputed components. Results will be combined using MIANALYZE SAS procedure with the Rubin's rules. Please refer to [Appendix 4](#) for detail SAS code.

---

Document:	\\ieedc-vnasc01\Biosdata\Archigen\SAIT101\YWA21301\Biostatistics\Documentation\SAP	Version Number:	V2.0
Author:		Version Date:	13Feb2019
Template No:	CS_TP_BS016 Revision 4	Reference:	CS_WI_BS005
Effective Date:	01Apr2016		

## 15.2. OTHER EFFICACY

### 15.2.1. SECONDARY EFFICACY VARIABLE(S) & DERIVATION(S)

#### Change from Baseline in DAS28-CRP at Week 8, 16, 36, and 52

Change from baseline in DAS28-CRP at week 8, 16, 36 and 52 will be derived with the similar criteria in Section 15.1.1 of this analysis plan.

#### ACR20 response rates at Week 8, 16, 24, 36, and 52

ACR20 response is defined as at least a 20% improvement from baseline if meet the criteria below. A subject will be classified as having achieved an ACR20 response (ACR20 = 1) if the following 3 conditions are satisfied.

$$\frac{\text{Swollen Joint Count at visit } X - \text{Swollen Joint Count at baseline}}{\text{Swollen Joint Count at baseline}} \leq -0.2 \text{ and}$$

$$\frac{\text{Tender Joint Count at visit } X - \text{Tender Joint Count at baseline}}{\text{Tender Joint Count at baseline}} \leq -0.2 \text{ and}$$

At least 3 of following conditions are satisfied.

- $\frac{\text{Patient's Pain at visit } X - \text{Patient's Pain at baseline}}{\text{Patient's Pain at baseline}} \leq -0.2$
- $\frac{\text{Patient's Global at visit } X - \text{Patient's Global at baseline}}{\text{Patient's Global at baseline}} \leq -0.2$
- $\frac{\text{Physician Global at visit } X - \text{Physician Global at baseline}}{\text{Physician Global at baseline}} \leq -0.2$
- $\frac{\text{HAQ-DI at visit } X - \text{HAQ-DI at baseline}}{\text{HAQ-DI at baseline}} \leq -0.2$
- $\frac{\text{CRP at visit } X - \text{CRP at baseline}}{\text{CRP at baseline}} \leq -0.2$

#### ACR50 response rates at Weeks 8, 16, 24, 36, and 52

ACR50 response is defined as at least a 50% improvement from baseline if meet the criteria mentioned in ACR20 above with using 0.5 instead of 0.2.

#### ACR70 response rates at Week 8, 16, 24, 36, and 52

ACR70 response is defined as at least a 70% improvement from baseline if meet the criteria mentioned in ACR20 above with using 0.7 instead of 0.2.

#### Individual components of the ACR improvement criteria on Day 1 and at Week 8, 16, 24, 36, and 52

- Swollen and tender joint count (66/68)
- Patient's assessment of pain
- Physician's global assessment of disease activity
- Patient's global assessment of disease activity
- Patient's assessment of disability (HAQ-DI)
- C-reactive protein level.

#### Major clinical response

---

Document:	\\ieedc-vnasc01\Biosdata\Archigen\SAIT101\YWA21301\Biostatistics\Documentation\SAP	Version Number:	V2.0
Author:		Version Date:	13Feb2019

Template No: CS\_TP\_BS016 Revision 4  
Effective Date: 01Apr2016

Reference: CS\_WI\_BS005

Major clinical response is ACR70 response for 24 consecutive weeks. Subjects who are ACR70 responders at Week 8, 16 and 24 will be classified as a major clinical responder at Week 24; responders at Week 24, 36 and 52 will be as a major responder at Week 52.

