#### **Other Efficacy Endpoints**

- Change from Baseline in DAS28 at Weeks 8, 16, 36, and 52
- ACR20 response rates at Weeks 8, 16, 24, 36, and 52
- ACR50 response rates and ACR70 response rates at Weeks 8, 16, 24, 36, and 52
- Individual components of the ACR improvement criteria on Day 1 and at Weeks 8, 16, 24, 36, and 52
  - Swollen and tender joint count (the 66/68 joint count system)
  - Patient's assessment of pain (assessed on 1 to 100 mm Visual Analogue Scale [VAS])
  - Physician's global assessment of disease activity (assessed on 1 to 100 mm VAS)

- Patient's global assessment of disease activity (assessed on 1 to 100 mm VAS)
- Patient's assessment of disability (Health Assessment Questionnaire-Disability Index [HAQ-DI])
- CRP level
- Change from Baseline DAS28-CRP at Weeks 8, 16, 24, 36, and 52
- Major clinical response (continuous ACR70 for at least 24 weeks)
- Clinical remission (defined by SDAI < 3.3) at Weeks 8, 16, 24, 36, and 52
- Proportion of patients with European League Against Rheumatism (EULAR) response (good response, moderate response or no response) at Weeks 8, 16, 24, 36, and 52

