The following laboratory assessments will be performed:

- Clinical chemistry, hematology, urinalysis and HBV DNA only when negative HBsAg and positive HbcAb at screening;
- PK and PD sample collection;
- Immunogenicity.

The following must be performed on **Day 57 ± 3 days (Week 8)**:

- Physical / Neurological examination;
- Documentation of concomitant medications;
- Assessment of AEs/SAEs/ADRs.

The following efficacy assessments will be performed:

- Patient's assessment: global VAS and HAQ-DI, including patient's pain VAS;
- Physician's assessment: global VAS;

- Joint assessment. Each of the 66/68 joints will be evaluated for tenderness and swelling.

The following laboratory assessments will be performed:

- Clinical chemistry, hematology, urinalysis and HBV DNA only when negative HBsAg and positive HbcAb at screening;
- IgG, IgM, IgA;
- CRP, ESR;
- PK and PD sample collection.

The following must be performed on **Day 85 ± 3 days (Week 12)**:

- Physical / Neurological examination;
- Documentation of concomitant medications;
- Assessment of AEs/SAEs/ADRs.

The following laboratory assessments will be performed:

- Clinical chemistry, hematology, urinalysis and HBV DNA only when negative HBsAg and positive HbcAb at screening;
- PK and PD sampling;
- Immunogenicity.

The following must be performed on **Day 113 ± 3 days (Week 16)**:

- Physical / Neurological examination;
- Documentation of concomitant medications;
- Assessment of AEs/SAEs/ADRs.

The following efficacy assessments will be performed:

- Patient's assessment: global VAS and HAQ-DI, including patient's pain VAS;
- Physician's assessment: global VAS;

- Joint assessment. Each of the 66/68 joints will be evaluated for tenderness and swelling.

The following laboratory assessments will be performed:

- Clinical chemistry, hematology, urinalysis and HBV DNA only when negative HBsAg and positive HbcAb at screening;
- IgG, IgM, IgA;
- CRP, ESR;
- PK and PD sample collection;
- Immunogenicity.

The following must be performed on **Day 141 ± 3 days (Week 20)**:

- Physical / Neurological examination;
- Documentation of concomitant medications;
- Assessment of AEs/SAEs/ADRs.

The following laboratory assessments will be performed:

- Clinical chemistry, hematology, urinalysis and HBV DNA only when negative HBsAg and positive HbcAb at screening;
- PK and PD sampling.

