### **3.6.1.3 Study Drug Administration Part B**

Patients with an inadequate response (<50% improvement from Baseline in both the swollen and tender joint counts) at Week 24 (Visit 12), will be eligible to receive a further course of two 1,000 mg i.v. infusions, one infusion at Week 24 (Day 1 of second course) and the second infusion at Week 26 (14 days after first dose of second course).

The following must be performed on **Day 169 ± 3 days (Week 24, Day 1 of the Second course of infusion)**:

Following must be performed:

- Physical examination and vital signs;
- Neurological examination;
- Documentation of concomitant medications;
- Assessment of AEs/SAEs/ADRs;
- Urine pregnancy test for applicable females administered the second course of the study drug;

The following efficacy assessments will be performed:

- Patient's assessment: global VAS and HAQ-DI, including patient's pain VAS;
- Physician's assessment: global VAS;
- Joint assessment. Each of the 66/68 joints will be evaluated for tenderness and swelling.

The following laboratory assessments will be performed:

- IgG, IgM, and IgA;

- Clinical chemistry, hematology, urinalysis and HBV DNA only when negative HBsAg and positive HbcAb at screening;
- CRP, ESR;
- PK and PD sampling;
- Immunogenicity.

The following must be also performed:

- Contact IXRS;
- Randomization;
- The first of the two infusions of the study drug (see Section 3.2.1), as per IXRS for eligible patients only.

The following must be performed on **Day 183 ± 3 days (Week 26, Day 15 of the Second course of infusion)**:

- Physical examination and vital signs
- Neurological examination;
- Documentation of concomitant medications;
- Assessment of AEs/SAEs/ADRs;
- Urine pregnancy test for applicable females administered the second course of the study drug;
- Contact IXRS;
- The second of the two infusions of study drug (see Section 3.2.1), as per IXRS, for eligible patients only.

The following assessments will be performed on **Day 253 ± 7 days (Week 36)**:

- Physical / Neurological examination;
- Document concomitant medications;

- Assessment of AEs/SAEs/ADRs.

The following efficacy assessments will be performed:

- Patient's assessment: global VAS and HAQ-DI, including patient's pain VAS;
- Physician's assessment: global VAS;
- Joint assessment. Each of the 66/68 joints will be evaluated for tenderness and swelling.

Laboratory assessments

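### The SAP's Week 24 rule for major clinical response documents 16 weeks of ACR70, not the defined 24, and no rule recognises a 28-week run that ends at Week 36

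*SAP*

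**What the plan says.** Protocol 2.3.2 lists the endpoint among the other efficacy endpoints as "Major clinical response (continuous ACR70 for at least 24 weeks"), with no visit attached. SAP 15.2.1 repeats the duration: "Major clinical response is ACR70 response for 24 consecutive weeks". It then turns this into two visit rules:

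- Week 24: "Subjects who are ACR70 responders at Week 8, 16 and 24 will be classified as a major clinical responder at Week 24".
- Week 52: "responders at Week 24, 36 and 52 will be as a major responder at Week 52".

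The ACR70 entry in the same SAP section fixes when response is observed: "ACR70 response rates at Week 8, 16, 24, 36, and 52". No rule ends at Week 36. SAP 2.6, which lists departures from the protocol, does not mention a shorter duration for this endpoint. SAP 2.6 and 3.2 also drop the separate Week 24 analysis in favour of one final analysis of the 52-week data.

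**The concern.** The definition and the Week 24 rule stand next to each other and appear to require different durations. Week 8 to Week 24 is two 8-week intervals, so the rule looks too short for a 24-week endpoint. The Week 52 rule looks long enough, so one endpoint name would carry two different requirements in adjacent rows of the same table.

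The Week 24 row would mix patients who go on to document 24 weeks with patients who never do. A patient with ACR70 at Weeks 8, 16, 24 and 36 but not Week 52 meets the definition on the scheduled visits, yet fails the Week 52 rule. That patient is labelled only in the Week 24 row and cannot be told apart there from one whose response ended after Week 24. Correcting the Week 24 row alone would leave that patient counted nowhere.

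Loss of ACR70 after Week 24 is plausible. An ACR70 responder at Week 24 has at least 70% improvement in both joint counts, whereas protocol 3.6.1.3 offers a second course to patients with under 50% improvement in both. Everyone the Week 24 rule accepts therefore falls outside the stated retreatment criterion. The documents give no rate of loss.

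**Working it through.** **Inputs.** Visit days and windows come from protocol Table 2 and sections 3.6.1.2 and 3.6.1.3: Week 8 = Day 57 ± 3; Week 16 = Day 113 ± 3; Week 24 = Day 169 ± 3; Week 36 = Day 253 ± 7; Week 52 = Day 365 ± 7. Required duration: 24 weeks = 168 days.

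**Formula.** Documented span = (day of last visit − day of first visit) / 7. The range subtracts or adds the sum of the two windows.

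| Visits | Nominal days | Weeks | Range with windows |
|---|---|---|---|
| 8 to 24 (Week 24 rule) | 169 − 57 = 112 | 16.0 | 106/7 = 15.1 to 118/7 = 16.9 |
| 24 to 52 (Week 52 rule) | 365 − 169 = 196 | 28.0 | 186/7 = 26.6 to 206/7 = 29.4 |
| 8 to 36 (no rule) | 253 − 57 = 196 | 28.0 | 186/7 = 26.6 to 206/7 = 29.4 |
| 16 to 36 | 253 − 113 = 140 | 20.0 | 130/7 = 18.6 to 150/7 = 21.4 |
| 36 to 52 | 365 − 253 = 112 | 16.0 | 98/7 = 14.0 to 126/7 = 18.0 |

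The 24 weeks cannot be reproduced from the Week 24 rule. The shortfall runs from 24 − 16.9 = 7.1 to 24 − 15.1 = 8.9 weeks. The smallest runs of consecutive visits that reach 24 weeks are Weeks 8, 16, 24, 36 and Weeks 24, 36, 52.

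**Could the clock start at Day 1?** (169 − 1)/7 = 24.0 weeks, which matches the number. But ACR70 is a 70% improvement from baseline, so it cannot be met at baseline, and no ACR assessment is scheduled between Day 1 and Week 8. The Week 52 rule starts its clock at an observed ACR70 visit.

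**Response patterns.** Five visits give 2^5 = 32 yes/no patterns. The seven that matter, in the order Weeks 8, 16, 24, 36, 52 (1 = ACR70):

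| Pattern | Longest documented run (weeks) | Week 24 rule | Week 52 rule |
|---|---|---|---|
| 11100 | 16.0 | yes | no |
| 11101 | 16.0 | yes | no |
| 11110 | 28.0 | yes | no |
| 11111 | 44.0 | yes | yes |
| 01111 | 36.0 | no | yes |
| 00111 | 28.0 | no | yes |
| 10111 | 28.0 | no | yes |

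Five of the 32 patterns document at least 24 weeks. The Week 52 rule catches 4 of them. The Week 24 rule accepts 4 patterns, of which 2 never pass 16.0 weeks. Adding a Weeks 8, 16, 24 and 36 rule to the Week 52 rule catches all 5 and admits none below 24 weeks.

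**Output affected.** The comparisons in SAP 15.2.3 and 15.2.5 cover 3 treatment pairs × 2 analysis sets = 6 for the Week 24 row, of which 2 pairs × 2 sets = 4 are exploratory. With a Wilson and a logistic-regression result each, that is up to 6 × 2 = 12 differences with confidence intervals, plus the per-arm proportions.

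**The case against.** Several points can be made for the plan.

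- *The rule is open.* The SAP names its visits beside the definition, the protocol gives no visit algorithm, and choosing visits is ordinary SAP detail. That is true, but a choice that shortens a defined duration is a change of endpoint and belongs in SAP 2.6.
- *The Week 8 to 36 responder is not lost today.* This stands. That patient carries the Week 24 label, so the present fault is over-inclusion in that row. What is missing is any rule that recognises the 28-week run itself; outright omission would follow only from correcting the Week 24 row alone.
- *The pattern counts say nothing about patients.* This also stands. Their frequencies are unknown and they assume complete data, whereas SAP 15.2.2 imputes nothing in the main analysis. They show what each rule can and cannot classify, no more.
- *The figure of 12 differences is a maximum.* Agreed. The Appendix 5 code returns missing limits where no usable treatment estimate exists.
- *The 16.9-week bound assumes visits in window,* while SAP 5.3 summarises by nominal visit. Agreed, but to reach 24 weeks the Week 8 to Week 24 interval would have to stretch by 168 − 112 = 56 days.
- *Any visit-based rule infers continuity between visits.* True of every rule here. It does not excuse first and last observations only 16 weeks apart.
- *It is one supportive endpoint with no margin or decision rule.* True, and the point is sized accordingly.

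**Conclusion.** The concern holds. The Week 24 rule documents 16.0 weeks of ACR70 (at most 16.9 for visits in window) under the name of a 24-week endpoint, and the shorter duration is undeclared. Because the final analysis uses 52-week data, the later visits that could confirm 24 weeks will be in hand when the row is produced. The Week 52 rule meets the definition. The 28.0-week run ending at Week 36 has no rule of its own.

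This rests on the protocol's scheduled days and windows, on counting duration from the first observed ACR70 visit to the last, and on treating response as continuous between consecutive positive visits. The number of patients affected cannot be stated, since the documents give no ACR70 rate. All arms are classified by the same rule, so no between-arm bias is claimed, and the PK and DAS28 conclusions do not depend on it.

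**What to change.** In SAP 15.2.1:

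1. Relabel the Week 24 row *ACR70 sustained Weeks 8 to 24*, or delete it.
2. Classify major clinical response only from consecutive scheduled visits spanning at least 24 weeks: at Week 36 from ACR70 at Weeks 8, 16, 24 and 36, and at Week 52 from the existing Weeks 24, 36 and 52 rule.
3. Record the change in SAP 2.6.

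Steps 1 and 2 belong together, so that a documented response ending at Week 36 is not dropped. The Week 36 and Week 52 rows will overlap, since a patient with ACR70 at all five visits is in both. If a single visit-free proportion is wanted, as the protocol's wording suggests, a flag for meeting either classification supplies it.

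The cost is one or two sentences of SAP text, one row label, one added derivation and a line in SAP 2.6. No new data are needed and the Week 52 derivation is unchanged.

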**Change from Baseline in DAS28-ESR at Week 8, 16, 24, 36, and 52**

- $DAS28-ESR = 0.56 \times \sqrt{TJC28} + 0.28 \times \sqrt{SJC28} + 0.7 \times \ln(ESR) + 0.014 \times GH$
- Change at Visit 24 = Value of DAS28-ESR at Visit 24 – Baseline value of DAS28-ESR

Where ESR: The Erythrocyte Sedimentation Rate (in mm/h); GH: The patient global health assessment (from 0=best to 100=worst).

If ESR=0, it will be adjusted as  $\ln(ESR+1)$  while calculating DAS28-ESR, i.e.  $\ln(1)=0$ .

**Clinical remission at Weeks 8, 16, 24, 36, and 52**

Clinical remission is defined as score of Simplified Disease Activity Index (SDAI) smaller than 3.3. SDAI is calculated as following formula.

- $SDAI = TJC28 + SJC28 + PtG (cm) + PyG (cm) + CRP (mg/dl)$

Where TJC28 means the number of tender joints (0-28), SJC28 means the number of swollen joints (0-28), CRP means the C-Reactive Protein concentration, PtG means Patient’s global assessment (from 0=best to 10=worst, 10 cm=100mm), PyG means Physician’s global assessment (from 0=best to 10=worst, 10 cm=100mm).

SDAI will be considered as missing if any of the above five components is missing.

**Proportion of patients with European League against Rheumatism (EULAR) response at Weeks 8 16, 24, 36, and 52**

The EULAR response will be derived using the DAS28-CRP. To be classified as responders, patients should have a significant change in DAS (at least >0.6 from Baseline) and also low current disease activity. Subjects will be classified as either good, moderate or non-responder based on the following table:

The EULAR response criteria using the DAS28			
	Improvement in DAS28 from Baseline		
DAS28 at endpoint	> 1.2	>0.6 and ≤1.2	≤0.6
≤3.2	Good	Moderate	None
> 3.2 and ≤5.1	Moderate	None	None
> 5.1	Moderate	None	None

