**Appendix 5 DAS28 and EULAR Response Criteria**

**DAS28** is a formula combining:

- Tender Joint Count (28 joints)
- Swollen Joint Count (28 joints)
- ESR (mm/hour) or CRP (mg/L)
- General Health - Patient's Global Assessment of Disease Activity (VAS)

$$\text{DAS28-CRP} = [0.56 \times \sqrt{(\text{TJC28})} + 0.28 \times \sqrt{(\text{SJC28})} + 0.36 \times \log_{\text{nat}}(\text{CRP}+1)] \times 1.10 + 1.15$$

A calculator is available online at the following website:

<http://www.das-score.nl/das28/DAScalculators/dascalculators.html>

A representation and example is given below:

Based on the DAS28 score, disease activity is classified as:

≤ 2.6	Remission
>2.6 ≤ 3.2	Low disease activity
>3.2 ≤ 5.1	Moderate disease activity
>5.1	High disease activity

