**EULAR response Criteria:**

Based on the DAS, response criteria have been developed, the EULAR response criteria. The EULAR response criteria include not only change in disease activity but also current disease activity. To be classified as responders, patients should have a significant change in DAS (at least >0.6 from Baseline) and also low current disease activity. Three categories are defined: good, moderate, and non-responders.

The EULAR response criteria using the DAS28			
	Improvement in DAS28 from Baseline		
DAS28 at endpoint	> 1.2	>0.6 and ≤1.2	≤0.6
≤3.2	Good	Moderate	None
> 3.2 and ≤5.1	Moderate	None	None
> 5.1	Moderate	None	None

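### The EULAR response table gives the same result for endpoint DAS28 of >3.2 to ≤5.1 and of >5.1, so the 5.1 cut-point does nothing, and the table disagrees with the sentence beside it

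*SAP*

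**What the plan says.** EULAR response (good, moderate or none) is listed in protocol Section 2.3.2 among the other efficacy endpoints, at Weeks 8, 16, 24, 36 and 52. SAP 15.2.1 fixes the score, "The EULAR response will be derived using the DAS28-CRP", and makes the table the operative rule: "Subjects will be classified as either good, moderate or non-responder based on the following table".

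The three rows of the SAP table are indexed by DAS28 at endpoint. The columns are improvement >1.2, >0.6 to ≤1.2, and ≤0.6. They read:

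- "≤3.2 Good Moderate None"
- "> 3.2 and ≤5.1 Moderate None None"
- "> 5.1 Moderate None None"

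Protocol Appendix 5 prints the same three rows.

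The SAP sentence leading into the table says that, to count as responders, "patients should have a significant change in DAS (at least >0.6 from Baseline) and also low current disease activity". Appendix 5 carries the same requirement and states the principle: "The EULAR response criteria include not only change in disease activity but also current disease activity". The activity bands in Appendix 5 label DAS28 >3.2 to ≤5.1 as "Moderate disease activity" and give >5.1 a separate label, high.

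Under SAP 15.2.3, EULAR response is summarised by visit with Wilson intervals and analysed by logistic regression, in both the FAS and the PP set. SAP 15.2.5 repeats the comparison for the other two treatment pairs.

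**The concern.** A table with three activity bands, two of which give the same answer in every column, is either redundant or contains a wrong cell. If the two upper bands were meant to be treated alike, a single row for DAS28 above 3.2 would have been enough. Appendix 5 keeps the two bands apart, which suggests that a distinction was intended and lost.

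The prose does not repair the table. In the Appendix 5 bands, low activity ends at 3.2. Read literally, the sentence beside the table allows response only at or below 3.2, yet the table scores Moderate in both upper bands when improvement exceeds 1.2.

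Because the SAP tells the programmer to classify from the table, it will be coded as printed. If a cell is wrong, the reported response rates at five visits, in two analysis sets and three treatment comparisons, will not be those of the criteria the table names.

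**Working it through.** **Step 1: compare the rows.** The plan states no figure to reproduce here, so the check is of the table itself. The rows for >3.2 to ≤5.1 and for >5.1 match in all three columns, in both documents.

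**Step 2: test the cut-point.** The table was coded as a function of endpoint DAS28 (190 values, steps of 0.05 from 0) and improvement (140 values, steps of 0.05 from −2), giving 190 × 140 = 26,600 points. Moving the 5.1 cut to 3.3, 4, 6 and 9 changed 0 classifications. The 3.2 cut does matter: it changes the category in two of the three columns.

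**Step 3: set the table against the sentence.** Low activity is taken as ≤3.2, from the Appendix 5 bands.

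| Endpoint DAS28 | Improvement | Printed table | Sentence, read literally |
|---|---|---|---|
| ≤3.2 | >1.2 | Good | responder |
| ≤3.2 | >0.6 to ≤1.2 | Moderate | responder |
| >3.2 to ≤5.1 | >1.2 | Moderate | not a responder |
| >3.2 to ≤5.1 | >0.6 to ≤1.2 | None | not a responder |
| >5.1 | >1.2 | Moderate | not a responder |
| >5.1 | >0.6 to ≤1.2 | None | not a responder |
| any | ≤0.6 | None | not a responder |

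Two cells conflict, both with improvement >1.2 and endpoint above 3.2. The literal sentence gives 5.1 no role either, so it cannot show where the rows ought to differ.

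**Step 4: which cells could separate the rows?** The ≤0.6 column is None by the change requirement. Good is confined to low activity. A worse endpoint should not earn a better category for the same improvement. Two candidates remain:

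- Cell A: endpoint >3.2 to ≤5.1, improvement >0.6 to ≤1.2, printed None. It would become Moderate.
- Cell B: endpoint >5.1, improvement >1.2, printed Moderate. It would become None.

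**Step 5: size, for illustration.** Inputs:

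- Mean improvement 1.9, the rituximab figure in protocol 1.3.2.
- SD of improvement s = 1.0, borrowed from the DAS28 SD in protocol 6.1; 1.5 is also tried, as an assumption.
- Baseline DAS28 normal with mean m = 5.0 to 7.0 and SD b = 0.8 to 1.0, independent of improvement. These are assumptions, since the documents give no baseline DAS28.
- 94 patients per arm.

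Endpoint is baseline minus improvement, and f is the normal density with mean 1.9 and SD s.

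- P(A) = ∫ from 0.6 to 1.2 of f(i) · [Φ((5.1 + i − m)/b) − Φ((3.2 + i − m)/b)] di
- P(B) = ∫ from 1.2 to ∞ of f(i) · [1 − Φ((5.1 + i − m)/b)] di

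The ceiling for cell A at s = 1.0 is the whole improvement band: Φ((1.2 − 1.9)/1.0) − Φ((0.6 − 1.9)/1.0) = Φ(−0.7) − Φ(−1.3) = 0.242 − 0.097 = 14.5%, and 94 × 0.1452 = 13.6 patients.

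| m, b, s | P(A) | of 94 | P(B) | of 94 |
|---|---|---|---|---|
| 5.0, 0.8, 1.0 | 10.9% | 10.3 | 0.6% | 0.6 |
| 6.0, 1.0, 1.0 | 7.0% | 6.5 | 9.5% | 8.9 |
| 7.0, 0.8, 1.5 | 1.5% | 1.4 | 19.7% | 18.5 |
| 7.0, 1.0, 1.0 | 2.4% | 2.3 | 28.7% | 27.0 |

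Over all the combinations, P(A) runs from about 1.5% to 10.9% and P(B) from 0.4% to 28.7%. At m = 6.0, b = 1.0, s = 1.0, good-or-moderate response as printed is about 76%. It would be about 83% if cell A became Moderate, and about 67% (76.3% − 9.5%) if cell B became None.

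**The case against.** The best defence is that redundant does not mean wrong. The table is complete, every patient falls in exactly one category, and current activity does count, through the 3.2 cut. That stands: the stated principle is weakened, not abolished, and the identical rows alone do not prove that a category is false.

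A reader might go further and infer that cell A must be the error, so that every patient ending at >3.2 to ≤5.1 after improving by >0.6 to ≤1.2 is misclassified as a non-responder. The documents do not support this. Cell B would separate the rows equally well, and scoring cell A as Moderate would add one more conflict with the sentence on low current activity. Nor can a cited source settle it: no EULAR publication is identifiable in the protocol references, in Appendix 5 as supplied, or in SAP Section 18.

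A reader might also take the point to concern patients with moderate activity at baseline. The rows index activity at endpoint. A patient who starts in the moderate band, improves by >0.6 to ≤1.2 and ends at ≤3.2 is scored Moderate.

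A fault in reading the PDF, such as merged cells, cannot be fully excluded. The same rows in both documents make it unlikely, though the SAP table looks copied from the protocol, so the two are not independent evidence. The conflict with the sentence in the >1.2 column also counts against a simple reading fault.

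**Conclusion.** The point holds in limited form. As printed, the 5.1 cut-point is inert in the rule that defines EULAR response, and table and sentence disagree on whether patients above 3.2 can respond. Which cell is wrong is not decided by the documents.

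The size depends on the answer. If cell A is wrong, about 1.5% to 11% of patients per arm would move from None to Moderate. If cell B is wrong, between under 1% and about 29% would move the other way. Both ranges rest on assumed baseline values, on independence of baseline and improvement, and on one mean improvement applied to a single visit. They show that the matter is not negligible; they do not predict the trial's rates.

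It would be wrong to infer a threat to the trial's main conclusions. The rule is the same in every arm, so no large bias between arms is expected, and no equivalence margin is stated for this endpoint. The five PK co-primary analyses, the DAS28 equivalence test and the sample size do not use the table. The point merits correction before programming, no more.

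**What to change.** Before EULAR response is programmed:

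1. Check the table in SAP 15.2.1 and in protocol Appendix 5 against the published EULAR criteria it names, looking first at the source PDFs for merged cells.
2. Correct whichever cell makes the two rows identical, in both documents.
3. Cite the source under the table.
4. Reword the sentence on low current disease activity so that it describes the table as corrected.

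The cost is one table cell, one sentence and one reference in each document. No new data are needed, since the DAS28-CRP components are already collected at all five visits. If outputs have already been programmed, the EULAR derivation and its tables need one rerun.
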